### OsrHSA Phase 1 study design schema

### 1.3 Schedule of Activities

- a. Screening procedures will be performed at screening visits from D-28 to D-2, including ultrasound, smoking, alcohol, drug use test, serum albumin. Pre-dose from D-1 to infusion, smoking, alcohol, drug use test, serum albumin will be performed again. (The two times serum albumin average will be used as subject's baseline serum albumin)
- b. Urine collection will be performed 24hr after infusion
- c. The 0.5h time point after dose initiation will change to  $\pm 5$  minute window (instead of  $\pm 2$  minute).
- d. The D3 and D5 time points will change to  $\pm 6$  hour window (instead of  $\pm 4$ h)
- e. Abdominal ultrasound exam will be performed and reviewed during the 28 day screening period, prior to patient check-in on Day -1
- f. Alcohol and Cotinine will be tested at all follow-up visits (D3, D5, D8, D15, D22, D30)
- g. Syphilis will be tested at the screening timepoint, in order to adhere to the new exclusion criteria described above
- h. Anti-HCP antibody will be measured at the same time points as ADA
- i. In order to calculate accurate creatinine clearance, subjects' body weight will be re-measured at Day 8 and Day 30 visits.
- j.

Table 1 Schedule of Activities

Protocol Activity	Clinical Research Unit (CRU) Confinement										Outpatient Visits					
	Screen -D28 to -D2	Pre-dose -D1 to dose	Dose initiation	0.5 h $\pm$ 5m after Dose initiation	1.0h $\pm$ 10m after Dose initiation	EOI+ 10m	0.5h Post EOI $\pm$ 10m	4h $\pm$ 10m	12h $\pm$ 10m	D2 24h $\pm$ 30m	D3 $\pm$ 6h	D5 $\pm$ 6h	D8 $\pm$ 1d	D15 $\pm$ 2d	D22 $\pm$ 2d	D30 $\pm$ 2d
Signed Informed Consent (ICF) 	×															
Inclusion/Exclusion Criteria	×	×														

Protocol Activity	Clinical Research Unit (CRU) Confinement										Outpatient Visits					
	Screen -D28 to -D2	Pre-dose -D1 to dose	Dose initiation	0.5 h ± 5m after Dose initiation	1.0h ± 10m after Dose initiation	EOI+ 10m	0.5h Post EOI ± 10m	4h ± 10m	12h ± 10m	D2 24h ± 30m	D3 ± 6h	D5 ± 6h	D8 ± 1d	D15 ± 2d	D22 ± 2d	D30 ± 2d
Demographics 	×															
Weight 	×	×							×	×		×				×
Medical History 	×	×								×	×	×	×	×	×	×
Physical Examination 	×	×				×	×	×	×	×	×	×	×	×	×	×
Current Medications/OTC/supplements	×	×											×			×
Vital Signs 	×	×		×	×	×	×	×	×	×	×	×	×	×	×	×
12 Lead Electrocardiogram (ECG) 	×	×			×	×	×	×	×	×	×	×	×	×	×	×

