Abdominal Ultrasound 	×															
Adverse Events (AE)	Ongoing															
Laboratory Tests																
Urine Drug Screen	×	×														
Alcohol Breath Test	×	×									×	×	×	×	×	×
Urine Cotinine Test	×	×									×	×	×	×	×	×
Pregnancy Test for Female 	×	×												×		×
Ig E and Ig G Against Rice	×							×			×	×		×		×
Hematology & Serum Chemistry 	×	×					×		×			×				×
Coagulation Tests	×											×				
Screening for HIV, HBV, HCV, Syphilis 	×															
Urine Analysis (U/A) 	×						×	×	×	×	×	×	×	×	×	×
Study Drug Administration			×													
Injection Site Reaction		×		×		×	×		×	×						
Pharmacokinetics (PK) 		×		×		×	×	×	×	×	×	×	×	×	×	×
Colloid Osmotic Pressure 		×		×		×	×	×	×	×	×	×	×	×	×	×
Anti-Drug Antibodies (ADA); Anti-HCP antibody 		×										×	×	×	×	×

**Abbreviations:** ADA = anti-drug antibody; EOI=End of Infusion; EOS=End of Study; EOT=End of Treatment; ECOG = Eastern Cooperative Oncology Group; ConMeds = Concomitant medications; CT = computed tomography; MRI = magnetic resonance imaging; HIV = human immunodeficiency virus; HBV = hepatitis B virus; HCV = hepatitis C virus; PD = pharmacodynamics; PK = pharmacokinetics

1. Written consent must be obtained prior to performing any protocol specific procedure.
2. Age, height, gender, ethnicity, and race at screening where possible.
3. Body weight will be measured at screening, predose and postdose at Day 2, D 3, Day 8 and Day 30 visits .. 24-hour liquid input (drinking water) and output (urine) will be recorded post EOI
4. Medical History: includes any significant or relevant diseases, surgeries, or other medical events during the past 5 years and any new conditions arising while enrolled in the study.
5. PE: Full physical examination including the cardiovascular, pulmonary, GI, and nerve system, and skin will be performed at screening and EOS visits, and partial physical examination can be done at other visits to assess any abnormalities or change from baseline, including focused skin and cardiopulmonary examination.

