6. Vital signs include temperature, pulse, respiratory rate, and blood pressure. Vital signs will be assessed at screening and on the visits at the clinical research unit. Vital sign will be performed within 30 minutes prior to the infusion, at the EOI (+ 5 minutes) and before every PK sampling. Additionally, blood pressure will be measured every 10 minutes during infusion, every 30 min post EOI up to 6 hours, every 1 hour after 6 hours up to 12 hours post EOI, and every 2 hours until 24 hours post EOI or discharge, and at every outpatient visit. Blood pressure should be measured prior to Colloid osmotic pressure sampling when blood pressure measuring and colloid osmotic pressure sampling are specified to be done at the same time.
7. ECGs (12 lead) will be collected at screening, predose, during infusion(1hr),and EOI, prior to PK sampling during Day 1, and as clinically indicated, and at EOS.
8. Abdominal ultrasound exam will be performed and reviewed during the 28 day screening period, prior to patient check-in on Day -1
9. Only in women of childbearing potential. Urine pregnancy test will be done at screening and EOS, serum pregnancy test will be done pre-dose and on D15, or as clinically indicated.
10. Hematology includes Complete blood count (CBC) (hematocrit (HCT), hemoglobin, red blood cells (RBC), Red Cell Distribution Width (RDW), Mean Corpuscular Volume (MCV), Mean Corpuscular Hemoglobin (MCH), Mean Corpuscular Hemoglobin Concentration (MCHC), platelets, white blood cells (WBC) with absolute differential counts of neutrophils, lymphocytes, monocytes, eosinophils, and basophils). Serum Chemistry ALT, AST, ALP, K+, Na+, Cl-, Ca2+, TBIL, blood urea nitrogen (BUN) or urea, creatinine, uric acid, glucose (non-fasted).
11. HIV screening (Antigen/antibody test), HCV antibodies, hepatitis B surface antigen (HBsAg), hepatitis B surface antibody (anti-HBs), total hepatitis B core antibody (anti-HBc), IgM antibody to hepatitis B core antigen (IgM anti-HBc), Syphilis.
12. Twenty-four hours urine for D1 after the administration will be collected for 24 hours urine protein. Dipstick is acceptable for other time points. Microscopic analyses if clinically indicated. If  $\geq 2+$  protein on urine dipstick, then collect spot urine sample to calculate urine protein to creatinine ratio (UPCR) or collect 24h urine.

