#### 3.2 Endpoints

##### Primary Endpoints

- 1) Safety and tolerability profile including adverse events, changes in safety assessment parameters (e.g. vitals, ECGs, clinical laboratory results)

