### 11.4.2 Safety Analysis

Safety data will be summarized by treatment group using descriptive statistics. No formal inferential analyses are planned for safety comparisons. Continuous safety data will be summarized as sample size, mean, SD, minimum, and maximum, by scheduled time point and treatment for observed values and change from baseline values (as appropriate). Tabulations of frequencies and proportions, as appropriate will be used for the evaluation of categorical (qualitative) safety data.

Adverse events will be classified by SOC and term using the Medical Dictionary of Regulatory Activities (MedDRA) coding dictionary. Incidence of treatment-emergent adverse events (TEAEs) will be summarized by SOC and preferred term for each treatment group. Incidence of TEAEs will also be summarized by severity and association with the study treatments.

Concomitant medications will be presented in summary tables and listings.

All safety data summaries will be based on the Safety Analysis Set. No statistical tests will be performed for the safety endpoints.

Missing data will be treated as they are. No imputations of missing data are planned.

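### Urinalysis has no pre-dose value: the only pre-treatment result is 2 to 28 days old, although urine is already collected pre-dose for other tests

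*Combined protocol and SAP*

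**What the plan says.** Table 1 in section 1.3 gives the row "Urine Analysis (U/A" one mark before treatment, at screening, and ten after dosing: 0.5h after end of infusion, 4h, 12h, Day 2, Day 3, Day 5, Day 8, Day 15, Day 22 and Day 30. The pre-dose column (Day -1 to dose) is blank.

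Item a above the table sets the windows: "Screening procedures will be performed at screening visits from D-28 to D-2", and then "Pre-dose from D-1 to infusion, smoking, alcohol, drug use test, serum albumin will be performed again". Urinalysis is not among the tests repeated. Section 4.2 and inclusion criterion 4 mention urinalysis only at screening.

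Note 12 adds that "Twenty-four hours urine for D1 after the administration will be collected for 24 hours urine protein" and that "Dipstick is acceptable for other time points". A dipstick of 2+ protein or more leads to a protein-to-creatinine ratio or a 24-hour collection.

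Two other urine tests are marked at both screening and pre-dose: "Urine Drug Screen" and urine cotinine.

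The primary endpoint (section 3.2) includes "changes in safety assessment parameters (e.g. vitals, ECGs, clinical laboratory results". Section 11.4.2 summarizes continuous safety data as "observed values and change from baseline values (as appropriate", and categorical safety data as frequencies and proportions. A baseline is defined only for serum albumin (item a).

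**The concern.** Urine is tested repeatedly after an albumin infusion, with a 24-hour protein collection and a work-up step for a positive dipstick, yet nothing records the urine finding at the time of dosing. Under section 7.1 all adverse events are recorded once dosing starts; before that, only serious events related to the study intervention are. Dosing is therefore the line between a pre-existing finding and an adverse event, and the protocol has no urinalysis close to that line.

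Section 10.1 counts a new abnormal laboratory finding, or the worsening of an old one, as an adverse event. Section 10.2 lists a temporal relationship among the grounds for judging an event related. If an abnormality arose between screening and check-in, the first post-dose urinalysis could show it as new, and no record would exist to say otherwise. What is at stake is the attribution of individual urinalysis findings within one component of the primary endpoint.

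**Working it through.** The plan states no figure to reproduce. The check is a count of table marks, an interval, and a comparison of rows.

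**1. Is the blank cell real?** Each row was read against the 16 visit columns. Study drug administration falls under dose initiation, as it must. The 13 marks in the PK row match note 13. Read the same way, the urinalysis row has 1 screening mark, 0 pre-dose marks and 10 post-dose marks.

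Two cautions apply. The weight row (12h, Day 2, Day 5, Day 30 after dosing) does not match note 3 (Day 2, Day 3, Day 8, Day 30), and the antibody row marks Day 5 where note 15 does not. The table is therefore not faultless. Item a is also not a complete list of pre-dose tests, since it omits vital signs and ECG, which are marked pre-dose. Its silence on urinalysis is weak evidence taken alone. Still, neither note 12 nor any other text supplies a pre-dose urinalysis.

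**2. Age of the reference value.** Screening runs from Day -28 to Day -2 and dosing is on Day 1. With no Day 0, the age at dosing is 28 days at most and 2 days at least. If a Day 0 were counted, it would be 29 and 3. Section 4.2 puts screening within 28 days before administration, which fits the first reading. A sample in the pre-dose window would be 0 to 1 day old.

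**3. What the ten marks mean.** Four of them (0.5h, 4h, 12h and 24h) overlap the 24-hour collection in note 12, which leaves 10 - 4 = 6 outpatient times (Day 3 to Day 30). Ten is the number of marked times, not necessarily of separate dipsticks.

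**4. Comparison with other rows.**

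| Test | Screening | Pre-dose | Post-dose marks |
|---|---|---|---|
| Hematology and chemistry | yes | yes | 4 |
| Urine drug screen | yes | yes | 0 |
| Urine cotinine | yes | yes | 6 |
| Coagulation | yes | no | 1 |
| Rice IgE and IgG | yes | no | 5 |
| Urinalysis | yes | no | 10 |

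Vital signs, ECG, weight and physical examination also have both pre-treatment marks. Of the tests without a pre-dose value, urinalysis is repeated most often. The pre-dose pregnancy test is a serum test (note 9), so the urine available at that visit is the sample for the drug screen and cotinine.

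**5. Numbers of subjects.** Table 2 has 5 cohorts of 8 (6 OsrHSA, 2 placebo): 5 × 8 = 40 in all, 5 × 6 = 30 on OsrHSA and 5 × 2 = 10 on placebo.

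**The case against.** The strongest reply is that nothing in the plan is contradicted. The screening urinalysis is a pre-treatment value, eligibility rests on it, and coagulation and rice antibodies rely on screening alone in the same way. That stands: this is a design choice that can be improved, not an inconsistency.

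The reply also limits what a reader might infer:

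- *That the placebo group cannot correct for background findings.* Subjects are randomized and follow one schedule, so background abnormalities add noise and no systematic bias between arms. Two placebo subjects per cohort are few, but there are 10 overall. The protection is partial, and it does not extend to judging a single subject.
- *That a dipstick half an hour after infusion would show a false treatment effect.* Note 12 assigns Day 1 to the 24-hour collection and accepts dipsticks at other times, so a dipstick at that mark is not established.
- *That change-from-baseline summaries would be distorted.* In section 11.4.2 these cover continuous data, and only as appropriate. Dipstick grades are ordinal and belong with the categorical tabulations.
- *That subjects with check-in proteinuria would be dosed against the rules.* No text makes such a finding a bar to dosing; inclusion criterion 4 refers to urinalysis at screening.
- *That apparent incidence would rise by a calculable amount.* The documents give no prevalence of abnormal urinalysis in volunteers who passed screening, so no such figure is supported.

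Finally, a negative pre-dose dipstick would not prevent chance positives at later visits. That is true, and placebo is the control for those. It does not answer the separate question of whether a finding was already present at dosing.

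**Conclusion.** The point holds as a low-cost improvement. Urinalysis has ten marked post-dose times and one pre-treatment value, 2 to 28 days old, while the main safety assessments beside it have a value at dosing. Under the protocol's own definitions, an abnormality present at check-in could be recorded as treatment-emergent and judged related, with no data to show otherwise.

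The consequence is limited to attribution in individual subjects and to shift and treatment-emergent tabulations of urinalysis. A reader might go further and infer that dose-escalation decisions are at risk. The documents do not show that: a DLT needs a related event of Grade 3 or above (section 4.2.1), and nothing links an ordinary dipstick finding to that grade.

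The conclusion rests on Table 1 as read, with the pre-dose cell blank, and on screening serving as the reference by default because no urinalysis baseline is defined. It needs no prevalence assumption.

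**What to change.** Mark urinalysis (dipstick) in the pre-dose column of Table 1, using the urine already collected for the drug screen and cotinine test. In section 11.4.2, name that result as the reference for shift and treatment-emergent tabulations of urinalysis. Note 12's existing 2+ step would then apply at this time point as at the others.

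The cost is one table cell, one sentence, about 40 dipsticks and an occasional protein-to-creatinine ratio. It assumes that the existing sample is sufficient for a dipstick. The reference age falls from 2 to 28 days to 0 to 1 day. The change does not give the 24-hour urine protein a baseline, and it does not remove chance positives at later visits.

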## 2 INTRODUCTION

### 2.1 Background

Human serum albumin (HSA), the main protein of human blood plasma, is a soluble, globular, and unglycosylated monomeric protein. It is responsible for 70-80% of colloid pressure of normal plasma, thus plays a primary role in regulating blood volume by maintaining the colloid osmotic pressure and stabilizing extracellular fluid volume. HSA also functions as a carrier protein for steroids, fatty acids, hormones, and small molecules (1).

Clinically, HSA is widely used for restoration and maintenance of circulating blood volume where volume deficiency has been demonstrated and use of a colloid is appropriate, such as adult respiratory distress syndrome, hypovolemia, large-volume paracentesis, ovarian hyperstimulation syndrome, plasma exchange, and ascites caused by cirrhosis of the liver (2, 3). Moreover, HSA is also used as an excipient for vaccines or therapeutic protein drugs and as a cell culture medium supplement in the production of vaccines and pharmaceuticals (4). Many other novel uses for HSA in biological applications have recently been explored, such as carrier of oxygen (5), nanodelivery of drugs (6), and fusion of peptides (7). Currently, clinical used production of HSA is primarily based on collected human plasma, which raises a public health concern with plasma-derived HSA (pHSA) with its potential risk for transmission of blood-derived infectious pathogens, such as bacteria (syphilis, Chagas disease), viruses (including but not limited to HBV, HCV, HIV, HTLV, West Nile virus, CMV) and prions (Mad Cow Disease) (9, 10). The market demand for HSA is estimated around 1000 (Human Serum Albumin Market In-deep Analysis and Experts Review Report 2019-2024) tons per year worldwide. It was reported that the shortage of human plasma led to a rapid increase in price of HSA, which in turn resulted in fake albumin appearing on the market (8). In fact, illegal plasma collection has caused HIV to spread rapidly, creating what are known as AIDS villages in Henan Province in China (11).

The development of screening has been greatly decreased the risk for transmission of blood-derived infectious pathogens, however, the risk has never been eliminated and is always there. To eliminate the potential risk of viral contamination, regulatory agencies in some have encouraged pharmaceutical companies to use non-animal-derived sources for pharmaceutical production (12). Thus, the development of a low-cost method for the production of recombinant HSA (rHSA) is essential as a safer and potentially unlimited alternative to pHSA.

Over the past decades, various expression systems have been used to produce rHSA, including *Escherichia coli* (13), *Saccharomyces cerevisiae* (14), *Kluyveromyces lactis* (15), *Pichia pastoris* (16), transgenic animals (17), and transgenic plants (18–21). Attempts to produce rHSA in tobacco leaves and potato tubers achieved expression levels of 0.02% of total soluble protein (TSP) (18), and expression was increased to 0.2% of TSP by targeting the rHSA to the apoplast of potato tubers (19). Recently, an expression level of 11.1% of TSP was obtained by expressing

rHSA in tobacco leaf chloroplasts (20). More recently, an rHSA expression level of 11.5% of total proteins was achieved in a rice cell culture by a sugar starvation-induced promoter (21). Although rHSA has been successfully expressed in these systems, none of them has proven to be cost-effective at large scale.

Plant seeds, especially cereal crop seeds, are promising vehicles for producing recombinant proteins, because they can achieve high accumulation of recombinant protein, display high levels of protein stability, stored for long periods of time, and are well controlled on a production scale (22, 23). Human lysozyme and lactoferrin produced for oral administration have been successfully expressed in rice seeds (24, 25). Here, Healthgen developed rice seeds as a bioreactor for large-scale production of *Oryza sativa* recombinant HSA (OsrHSA). OsrHSA can be highly and stably expressed in rice seeds and can be processed cost-effectively. OsrHSA was found to be equivalent to pHSA in terms of biochemical properties, physical structure, functions, and immunogenicity.

## **2.3 In summary, the risk/benefit balance is considered acceptable to administer OsrHSA to healthy volunteers. Preclinical Studies**

### **2.3.1 Non-clinical Pharmacology**

The nonclinical pharmacology program for OsrHSA has been designed to evaluate the *in vivo* efficacy, immunopharmacological activity and safety profiles in animals to predict the pharmacologic profile of OsrHSA in human. The *in vivo* efficacy of OsrHSA was evaluated in the treatment of ascites of high-fat diet induced hepatic cirrhosis in a Wistar rat model, as well as in hemorrhagic shock model using male Japanese rabbits. Similar efficacy of OsrHSA and HpHSA has been demonstrated in these two animal disease models.

The effects of OsrHSA on the immune function of mammalian systems were investigated in three studies. No active systemic anaphylaxis (ASA) reaction was induced in rabbits, after primed with OsrHSA/CFA and challenged with OsrHSA/IFA, with no elevated total IgG, IgM, IgA, IgE production detected. No passive cutaneous anaphylaxis (PCA) induced in the guinea pigs after transfer the sensitized serum from the rabbits. 1/1436 and 0/200 anti-HCP IgE antibody was detected in a preliminary non GLP study and an US-GLP study, suggesting a low risk of the HCP from *Oryza sativa* in inducing allergic responses in humans. T-cell mediated DTH study confirmed that OsrHSA and HpHSA were weakly immunogenic in soluble forms as a foreign antigen to mice. If administered as soluble proteins, OsrHSA was unable to induce DTH response in mice, which suggested a low risk of inducing type IV hypersensitivity in human subjects.

### **2.3.2 Non-clinical Pharmacokinetics**

The pharmacokinetic (PK) and toxicokinetics (TK) profiles of OsrHSA were characterized in rats and monkeys following intravenous administration, which is the intended route of administration in human. In order to distinguish exogenous OsrHSA from endogenous rat serum albumin, OsrHSA was labeled with I by Chloramine-T method before administration.

Distribution, metabolism and excretion was evaluated in the single-dose PK study in rats. OsrHSA is expected to behave like HSA, an endogenous protein, in drug transportation as well as in interactions with CYP enzymes or other drug transporters. Therefore, no pharmacokinetic drug interaction studies of OsrHSA were conducted.

HpHSA was included as a benchmark control and compared with OsrHSA side-by-side in several pharmacokinetic and toxicokinetics studies. HpHSA and OsrHSA showed similar PK and TK profile among all the studies, except HpHSA showed stronger immunogenicity in rats following repeat dose administration.

### 2.3.3 Safety Pharmacology and Toxicology

Safety pharmacology was conducted in mice to evaluate the effect on CNS function, as well as in cynomolgus monkeys to evaluate the effect on cardiovascular and respiratory functions. HpHSA was included as a control in all these studies to detect off-target or impurity induced side effects.

Because of pre-clinical and clinical experiences over many years of using with HpHSA, the full battery of toxicology studies conducted were not to evaluate the pharmacological and toxicological effects of the active ingredient albumin in OsrHSA, but mainly to evaluate unexpected toxic activities due to the impurities in the OsrHSA drug product. Evaluation of the potential risk to humans receiving OsrHSA was conducted in a series of US-GLP compliant toxicology studies according to 21 CFR 58.

While albumin are variable among the species, the tertiary structures and biological functions are highly conserved (Nurdiansyah, R., Rifa'I, M. 2016). Since the MOA of albumin for treatment of circulatory dysfunction is attribute to the increase of plasma volume, which is similar among species, therefore, multiple species (both rodent and non-rodent) were included in the toxicology evaluation.

Single-dose study in rats, 2-week repeat-dose with 4-week recovery phase studies in rats and monkeys were conducted to assess the toxicity and toxic organs as well as the reversibility, persistence, or delayed occurrence of any safety findings. Among these studies, the toxic levels and toxic organs identified were similar in animals treated OsrHSA and HpHSA. The treatment-related clinical and pathological changes were directly resulted from the biologic functions of albumin, and the daily injection induced fluid overload and increased blood pressure. No OsrHSA specific toxicity was identified, indicating the entire formulation of OsrHSA, including all possible impurities, exerted similar biological function, as well as toxicity at high dose, as that of the formulation of HpHSA. Both OsrHSA and HpHSA were immunogenic in animals via *i.v.* dosing. Formation of ADA was prevalent in rats and monkeys, although no impact on TK or systemic exposures were observed. Regardless with HSA formulation administered, ADA formed can be cross-recognized by the other HSA reagent, indicating that these ADA were against the same epitopes common in both OsrHSA and HpHSA, further supported the tertiary structure similarity between OsrHSA and HpHSA.

A full battery of study was conducted to evaluate the genotoxicity of OsrHSA as required in ICH S2 (R1) on Genotoxicity testing and Data Interpretation for Pharmaceuticals Intended for Human Use, June 2012. Ames test, chromosomal aberration test as well as *in vivo* micronucleus study confirmed that OsrHSA has no potential genotoxicity.

Host cell protein (HCP) is the main impurity in the formulations of OsrHSA. The potential toxicity and immunogenicity induced by HCP was evaluated in a 2-week daily repeat *i.v.* dose non-GLP study in SD rats. No clinical findings were observed for 25 µg/kg HCP, that is equivalent to the possible HCP presented in 5 g/kg OsrHSA.

